2.3 RISK/BENEFIT ASSESSMENT

2.3.1 KNOWN POTENTIAL RISKS

No more than minimal risks are expected to participants enrolled in this trial. The discomforts/risks are listed below:

Immediate discomforts/risks:

1. Discomfort related to refraining from tooth brushing from the previous night until the morning of rinses and sampling collection. This is expected to be a common discomfort (incidence > 25%). The subject may feel malodor in the morning of the test due to the suspension of oral hygiene. After the sampling is completed, the subject will receive a professional cleaning or supervised toothbrushing to remove remnants of dental plaque.
2. Discomfort related to collecting saliva samples. This is expected to be a likely discomfort (10-25%), as some individuals do not feel comfortable in spitting saliva into a tube. This discomfort will be minimized by maintaining the subject in a private dental chair, with only the trained study staff offering instructions on the procedure.

3. Discomfort related to rinsing with unflavored rinses. This is expected to be a likely discomfort (10-25%), as the rinses will be prepared from reagent grade chemicals, with no flavoring agents.
4. Discomfort related to refraining from eating or drinking for up to 2 hours during the collection of samples. This is expected to be a likely discomfort (10-25%). This may be more disturbing for individuals with reduced saliva flow, if they are used to sip water constantly. If the subject (especially those with dry mouth) feel the need of drink water during the two-hour period after the rinse, he/she will be allowed to do so, and notes taken as protocol deviation in order to later assess their effect on the study outcomes.

Long-range risks:

1. Loss of confidentiality of the study records. This risk is expected to be rare. To minimize the risk of confidentiality breach, data will be stored in password-protected electronic files or locked storage cabinets accessible only to the study personnel. Standards for data collection, management and analysis will be followed.

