5.2 EXCLUSION CRITERIA

An individual who meets any of the following criteria will be excluded from participation in this study:

1. Unable to understand and/or follow study instructions
2. Active periodontitis
3. Oral pain
4. In need of urgent dental care

LIFESTYLE CONSIDERATIONS

During this study, participants are asked to:

- Use a standardized toothpaste and toothbrush, provided by the study team at the first visit, to level the background exposure to fluoride, 7 days prior to each experimental phase
- Refrain from using any other mouth rinse or professional products during the study period
- Refrain from drinking green or black tea (which have high fluoride concentration) on the night before or the day of their visits
- Refrain from brushing their teeth on the night before and the morning of tests/sampling
- Refrain from eating or drinking for 2 hours after the rinses, during which saliva and dental plaque will be sampled

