6.1.2 DOSING AND ADMINISTRATION

All participants will test both intervention groups; half of them will test the groups in one order (1->2), the other half in the other order (2->1). The order will be determined randomly using a computer-generated randomization list in MS Excel.

Each intervention group will be tested in one experimental phase, spaced at least 7 days from the following phase to avoid any interference with the previous treatment [Fernández et al., 2015].

No treatment will be performed by the patient at home; both interventions will be delivered by the study team at the study visits.

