6.3 MEASURES TO MINIMIZE BIAS: RANDOMIZATION AND BLINDING

Blinding of the volunteers or clinical staff will not be possible because one of the treatments involves one rinse, the other involves two rinses. Nevertheless, the laboratory analyst will be blind with respect with the samples to be analyzed; for this, the samples will be coded with the participant ID and treatment phase (1st or 2nd, not to be confounded with treatment A or B; the treatment to be used in each phase will be determined randomly for each volunteer).

The order in which the two intervention groups will be tested will be randomized using the MS Excel, using a randomization table containing 3 columns with 20 rows:

1. First column: participant ID number, from 1 to 20
2. Second column: letters A or B (to represent the 2 intervention groups; 10 of each letter)
3. Third column: random numbers created using Excel function "rand"

The third and second column will be selected and sorted by the third column; this will randomize the treatment to be used in the first phase, according to the participant ID. The other intervention group will be tested in the following phase.

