7.2 PARTICIPANT DISCONTINUATION/WITHDRAWAL FROM THE STUDY

Participants are free to withdraw from participation in the study at any time upon request.

An investigator may discontinue or withdraw a participant from the study for the following reasons:

- Significant study intervention non-compliance
- If any clinical unanticipated adverse event (AE) occurs such that continued participation in the study would not be in the best interest of the participant
- Disease progression (oral or general) which requires discontinuation of the study intervention
- If the participant meets an exclusion criterion (either newly developed or not previously recognized) that precludes further study participation

The reason for participant discontinuation or withdrawal from the study will be recorded on the Discontinuation Case Report Form (CRF). Subjects who sign the informed consent form and are randomized but do not receive the study intervention may be replaced. Subjects who sign the informed

consent form, and are randomized and receive the study intervention, and subsequently withdraw, or are withdrawn or discontinued from the study will not be replaced.

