9.2 SAMPLE SIZE DETERMINATION

Data from Souza et al., 2016, using rinses similar to be used in this study, were used in sample size calculation. In that study, analysis of fluoride concentration in dental biofilm 10 h after using the rinses was available. (Note that the expected differences between the groups up to 2 h after the mouth rinsing are expected to be bigger, as saliva production overtime tends to clear all substances from the mouth).

Considering an 80% power to detect differences at the 5% significance level, an estimated sample size of 15 was determined (Stata/SE 15.1 for Mac). The sample size was increased to 20 subjects considering an attrition of 30%.

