9.4.2 ANALYSIS OF THE PRIMARY EFFICACY ENDPOINT(S)

Fluoride concentration in dental biofilm (primary efficacy endpoint) will be determined from the samples collected at baseline and 15 min, 60 min and 120 min (± 5 min) after rinsing with the assigned mouth rinse(s). The concentration at each individual timepoint will be compared between the two intervention groups. Also, the area under the curve of fluoride concentration in dental biofilm versus time will be calculated. This single measurement of fluoride bioavailability overtime after the mouth rinse(s) will be compared between the two intervention groups.

Each set of data will be checked for normality of errors. If the data is not normal, it will be log-transformed. An analysis of variance will be conducted, considering as factors the participant (experimental block) and the treatment. The use of the participant as a source of variation aims solely to reduce unknown variability in the error. An alpha level of 5% will be used to determine significant differences between the two groups.

In case data were log-transformed to fit the statistical analysis, their geometric means and confidence intervals (calculated from the log-transformed data) will be presented.

If data is missing from one of the intervention groups, the rest of the participant data (from the other intervention) will be excluded from the analysis.

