9.4.3 ANALYSIS OF THE SECONDARY ENDPOINT(S)

Fluoride and calcium concentrations in saliva (secondary endpoints) will be determined from the samples collected at baseline and 16 min, 30 min, 61 min, 90 and 121 min (± 5 min) after rinsing with the assigned mouth rinse(s). The concentration at each individual timepoint will be compared between the two intervention groups. Also, the area under the curve of fluoride and calcium concentration in saliva versus time will be calculated and compared between the two intervention groups.

Calcium concentration in dental biofilm (primary efficacy endpoint) will be determined from the samples collected at baseline and 15 min, 60 min and 120 min (± 5 min) after rinsing with the assigned mouth

rinse(s). The concentration at each individual timepoint will be compared between the two intervention groups. Also, the area under the curve of calcium concentration in dental biofilm versus time will be calculated and compared between the two intervention groups.

Each set of data will be checked for normality of errors. If the data is not normal, it will be log-transformed. An analysis of variance will be conducted, considering as factors the participant (experimental block) and the treatment. The use of the participant as a source of variation aims solely to reduce unknown variability in the error. An alpha level of 5% will be used to determine significant differences between the two groups.

In case data were log-transformed to fit the statistical analysis, their geometric means and confidence intervals (calculated from the log-transformed data) will be presented.

If data is missing from one of the intervention groups, the rest of the participant data (from the other intervention) will be excluded from the analysis.

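### The crossover ANOVA leaves out period, which costs power if a period effect exists and shifts the treatment estimate if completers are unequal by sequence

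*Combined protocol and SAP*

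**What the plan says.** **Design.** Section 6.1.2 sets a two-period crossover in which "half of them will test the groups in one order (1->2), the other half in the other order (2->1"). Section 6.3 builds the list with 10 participants starting on each intervention and says that "the samples will be coded with the participant ID and treatment phase". Phase is therefore a recorded design factor.

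**Model.** Section 9.4.2 states: "An analysis of variance will be conducted, considering as factors the participant (experimental block) and the treatment". Section 9.4.3 uses the same model, "considering as factors the participant (experimental block) and the treatment". Section 9.4.1 adds participants as blocks, one-tailed tests and a 5% level, but no period or sequence factor.

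**Who is analysed.** Section 9.3 limits the primary and secondary analyses to participants who complete the whole study. Sections 9.4.2 and 9.4.3 drop a participant's other phase when one is missing. Section 7.2 says that participants who "are randomized and receive the study intervention, and subsequently withdraw, or are withdrawn or discontinued from the study will not be replaced". Section 9.2 plans for substantial loss: "The sample size was increased to 20 subjects considering an attrition of 30" percent.

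**What might differ between phases.** Section 2.3.1 says: "After the sampling is completed, the subject will receive a professional cleaning or supervised toothbrushing to remove remnants of dental plaque". The schedule in section 1.3 lists no cleaning before phase 1. Against this, the lifestyle rules under section 5.2 standardise toothpaste and toothbrush "to level the background exposure to fluoride, 7 days prior to each experimental phase". The spacing of at least 7 days in section 6.1.2 is there to prevent interference from the previous treatment. That is carryover, not a period effect.

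**The concern.** In a two-period crossover the design factors are participant, period and treatment. The plan includes participant in order to reduce error variability, and the same argument applies to period.

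A period effect is possible here. Phase 2 biofilm forms after the cleaning or supervised brushing that ends phase 1, and after possibly longer use of the study toothpaste. No baseline adjustment is stated, so a change in background fluoride between phases would enter the outcome directly.

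Two things could follow if such an effect exists:

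- With equal numbers of completers in the two sequences, the treatment estimate stays unbiased. The period effect is counted as error, so the confidence interval widens, the test becomes conservative and power falls.
- With unequal numbers, part of the period effect is also added to, or taken from, the treatment estimate. Completer-only analysis without replacement makes unequal numbers likely, and with 15 completers an equal split is impossible.

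**Working it through.** **Inputs from the plan.** 15 evaluable participants, 80% power and a 5% level (9.2); one-tailed tests (9.4.1); 10 per sequence (6.3); attrition of 30% (9.2).

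**The plan's own figure.** Inflation: 15 × 1.3 = 19.5, rounded up to 20, which matches. With 30% actually lost, 20 × 0.7 = 14 complete, so results are given for 14, 15 and 20 completers. The 15 itself cannot be reproduced, because section 9.2 gives no effect size or SD. Solving a paired t test for 80% power at n = 15 gives a standardised effect of 0.675 (one-sided 5%) or 0.778 (two-sided 5%). Section 9.2 does not state sidedness; 0.675 is used below because the planned tests are one-tailed.

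**Assumptions that the documents do not give.** The true effect τ is 0.675 SD of the within-participant difference. The period effect π (phase 2 minus phase 1) is 0.25, 0.5 or 1.0 of the same SD. Completers are lost at random from 10 + 10.

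**Formulas.** Take each participant's difference, calcium prerinse minus fluoride only. Its mean is τ + π in the n1 participants who have the prerinse second and τ − π in the n2 who have it first.

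- Participant + treatment is a one-sample t test on all differences. Its estimate has mean τ + π(n1 − n2)/(n1 + n2), and the spread due to π stays in the error.
- Participant + period + treatment averages the two sequence means, on n − 2 degrees of freedom. It is unbiased for τ at any split.

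**Shift in the estimate.** 8/7: (8 − 7)/15 = 0.07π. 9/6: 3/15 = 0.20π. 10/5: 5/15 = 0.33π. 9/5: 4/14 = 0.29π.

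**How likely each split is** (hypergeometric, both directions together):

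- 14 completers: 7/7 37.2%, 8/6 48.8%, 9/5 13.0%, 10/4 1.1%.
- 15 completers: 8/7 69.7%, 9/6 27.1%, 10/5 3.3%.

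**Power, averaged over splits** (simulation, one-sided 5%), without / with the period term:

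| Completers | π = 0.25 SD | π = 0.5 SD | π = 1.0 SD |
|---|---|---|---|
| 14 | 75.4% / 76.1% | 69.8% / 76.1% | 51% / 76% |
| 15 | 78.2% / 79.1% | 73.0% / 79.2% | 54% / 79% |
| 20 (10/10) | 88.7% / 89.6% | 85.5% / 89.7% | 70% / 90% |

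**Type I error at π = 0.5 SD.** Without the term the average is 3.8% at 14 or 15 completers and about 3.3% at 20. Given a 9/5 split it is about 9.3% in one direction and 1.0% in the other. Given 9/6 it is 7.2% and 1.4%. With the term it is 5% at every split.

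**Confidence interval.** For equal sequences the expected variance of the differences without the term is 1 + π²n/(n − 1). At n = 20 and π = 0.5 this is 1 + 0.25 × 20/19 = 1.263, and its square root is 1.124. After allowing for the one degree of freedom, the 95% interval is about 12% wider without the term. At π = 0.25 it is about 3% wider.

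**Cost if π = 0.** Adding the term lowers average power by 1.2 points at 14 completers, 0.9 at 15 and 0.1 at 20. By split the loss is 0.3 to 0.4 points at 7/7 or 8/7, about 1.7 at 9/6, 3.5 at 9/5 and about 4.6 at 10/5.

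**The case against.** The strongest reply is that nothing in the documents shows a period effect, and the plan works against one. Toothpaste is standardised before each phase, other rinses and tea are restricted, brushing stops the night before each test, and phases are at least 7 days apart. Supervised toothbrushing is close to ordinary brushing.

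The period effects assumed are also large beside the treatment effect: 0.5 SD is 74% of 0.675 SD, and 1.0 SD exceeds it. Break-even at 14 completers is near 0.2 SD; below that the planned model has slightly more power.

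The treatment effect may be larger than 0.675 SD, since section 9.2 expects bigger differences within 2 h than in the 10 h data behind the sample size. With τ = 1.0 SD and π = 0.5 SD, power is 94.7% without and 96.7% with the term at 14 completers. At τ = 1.5 SD it exceeds 99% either way.

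Finally, inflated type I error needs both a material period effect and an unequal split in the harmful direction. At 14 completers, 9/5 or worse has a probability of about 7% each way. Participants randomised but not treated may be replaced, which limits imbalance.

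All of this stands, and it limits the size of the problem. It does not justify the omission: the plan cannot know in advance that π is below 0.2 SD, the protection is cheap, and choosing between the two models after seeing the data would be worse than either.

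**Conclusion.** The concern holds. No part of section 9.4 includes period, and neither the washout nor the toothpaste rule replaces a period term.

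The expected harm is modest and mainly a loss of precision. For a 0.5 SD period effect, power is about 6 points lower at 14 or 15 completers and about 4 points lower at 20, with an interval about 12% wider. For 0.25 SD the loss is under 1 point. Under the planned 10/10 balance the analysis is unbiased and conservative; bias and a type I error above 5% arise only given an unequal split in one direction.

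These sizes depend on the back-solved 0.675 SD effect, on assumed period effects and on random loss of completers. The omission itself and the shift formula depend on none of these. The point should be fixed, but it does not undermine the trial.

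**What to change.** In sections 9.4.2 and 9.4.3, specify the model as (log) outcome = participant + period + treatment, with period (phase 1 or 2) as a fixed factor. Report the treatment ratio and its confidence interval from that model, and report the number of completers in each sequence.

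The change needs SAP wording and one error degree of freedom. Phase is already coded on each sample, so no new data or visits are needed. The statistical price is the small loss of power shown above when there is no period effect; it is largest if the completer split turns out very unequal.

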4.4 END OF STUDY DEFINITION

A participant is considered to have completed the study if he or she has completed all phases of the study including the last visit or the last scheduled procedure shown in the Schedule of Activities (SoA), Section 1.3.

The end of the study is defined as completion of the last visit or procedure shown in the SoA in the trial globally.

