9.3 POPULATIONS FOR ANALYSES

For the primary and secondary outcomes, only participants completing the whole study will provide data for the analyses (per-protocol analysis).

For the tertiary outcomes, a modified intention-to-treat analysis will be used; all volunteers completing the fluoride-only mouth rinse treatment will provide data for the correlation analyses, even if they did not complete the other study treatment.

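### Read literally, the completer-only population and the missing-data sentence discard intact within-person pairs; exclusion should stop at the affected timepoint and phase

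*Combined protocol and SAP*

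**What the plan says.** For the primary and secondary endpoints, section 9.3 states that "only participants completing the whole study will provide data for the analyses (per-protocol analysis". Section 4.4 defines a completer as someone who has "completed all phases of the study including the last visit or the last scheduled procedure" in the schedule of activities.

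Section 9.4.2 plans several comparisons: "The concentration at each individual timepoint will be compared between the two intervention groups", followed by a comparison of the area under the concentration-time curve (AUC). Each uses an analysis of variance "considering as factors the participant (experimental block) and the treatment". The section closes with the missing-data rule: "If data is missing from one of the intervention groups, the rest of the participant data (from the other intervention) will be excluded". Section 9.4.3 repeats it for the secondary endpoints.

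Under section 7.2, participants who are randomised and treated and who "subsequently withdraw, or are withdrawn or discontinued from the study will not be replaced". Section 9.2 asks for 15 participants and enrols 20 to allow for 30% attrition. For the tertiary analyses, 9.3 is more generous: "all volunteers completing the fluoride-only mouth rinse treatment will provide data for the correlation analyses".

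The plan does not say whether the exclusion works by timepoint, by biofilm phase, by endpoint or by participant. It also does not say how an AUC is formed when a timepoint is missing.

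**The concern.** Three kinds of missing data fall under these rules, and they have different consequences.

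- **Early departure from Visit 3.** A participant who takes both rinses and leaves after the 60-min biofilm sample has baseline, 15-min and 60-min pairs in both phases. On the natural reading of 4.4 this person is not a completer, so 9.3 removes all of those pairs.
- **One failed sample or assay.** Completion in 4.4 is defined by visits and procedures, so a failed assay does not by itself make a non-completer. The closing sentence of 9.4.2 may still remove the participant, depending on its scope.
- **Withdrawal between the two treatment visits.** Only one treatment is observed and no pair exists.

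In the first two cases the discarded pairs are fully informative for the planned comparison. At stake is precision in a trial sized at 15 evaluable participants, and an analysis set that could change after the data are seen, because the wording allows more than one reading.

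**Working it through.** **1. The plan's own numbers.** 15 × (1 + 0.30) = 19.5, rounded up to 20, which reproduces the enrolled number in 9.2. But 30% attrition from 20 leaves 20 × 0.70 = 14 pairs, one short of 15. (Dividing instead, 15 / 0.70 = 21.4, gives 22.) There is no slack for lost samples beyond the planned attrition.

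The figure of 15 itself cannot be reproduced, since no effect size or standard deviation is given. If the true effect gives exactly 80% power at 15 pairs (standardised paired difference 0.675 one-sided, 0.778 two-sided), power is 77.3% / 76.8% at 14 pairs, 70.8% / 69.0% at 12 and 62.8% / 59.3% at 10.

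**2. Early leaver.** Section 8.1 schedules biofilm at baseline, 15, 60 and 120 min at each visit, so there are 4 pairs per phase and 8 over fluid and solid. Leaving Visit 3 after the 60-min sample costs 1 pair per phase. The completer rule removes all 4 per phase, so 6 intact pairs of 8 are discarded.

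**3. Failed samples.** The documents give no failure rate. Assume an independent rate m per result, with m = 2% or 5%. If k results are all needed, the share dropped is 1 − (1 − m)^k and the number left is N(1 − m)^k.

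| Scope of exclusion | k | Dropped, 2% / 5% | Left of 20 | Left of 14 |
|---|---|---|---|---|
| One timepoint pair, one phase | 2 | 4.0% / 9.8% | 19.2 / 18.1 | 13.4 / 12.6 |
| AUC, one phase (4 timepoints × 2 visits) | 8 | 14.9% / 33.7% | 17.0 / 13.3 | 11.9 / 9.3 |
| Any biofilm fluoride result (4 × 2 × 2 phases) | 16 | 27.6% / 56.0% | 14.5 / 8.8 | 10.1 / 6.2 |

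The last column applies if the 30% attrition occurs as well; if that allowance is meant to cover failed samples, use the column before it.

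**4. Participants with one treatment only.** Take 14 pairs and 6 unpaired participants, 3 per treatment. With participants as fixed blocks, using everyone gives 34 observations and 20 + 1 parameters, so 13 residual degrees of freedom. Using pairs only gives 28 observations and 14 + 1 parameters, again 13. Each unpaired observation is absorbed by its own block, and a numerical fit gave the same estimate and standard error both ways.

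With random participants and within-participant correlation r, effective pairs = 14 + 6(1 − r)/2. For r = 0, 0.5, 0.8 and 0.9 this is 17.0, 15.5, 14.6 and 14.3. The standard error falls by 9%, 5%, 2% and 1%.

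**5. What an all-data model needs.** Samples from one visit share that visit's conditions. Let the visit variance be v times the residual variance (assumed), with 20 participants, 2 visits and 3 post-rinse times. The treatment mean square then has an expected error part of 1 + 3v. A model with only a participant random effect has 120 − 25 = 95 residual degrees of freedom. Of these, 19 have expectation 1 + 3v and 76 have expectation 1, so it uses 1 + 3v × 19/95 = 1 + 0.6v. The test statistic is too large by √[(1 + 3v)/(1 + 0.6v)], which is 1.23, 1.39 and 1.58 for v = 0.25, 0.5 and 1. A nominal one-sided 5% test of the average treatment effect would reject about 9%, 12% and 15% of the time under no effect. A participant-by-visit term is therefore needed.

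**The case against.** The strongest reply is that 9.4.2 analyses each timepoint and each data set separately, so its closing sentence may mean only that each comparison uses complete pairs. That is a fair reading, and a failed sample then costs 4.0% or 9.8% per comparison. It does not rescue the early leaver, whom 9.3 removes whatever 9.4.2 means. It also leaves the AUC without a rule for an incomplete curve. The wording of 4.4, which links the last visit and the last procedure with an or, might let a lenient analyst count the early leaver as a completer; the plan should not depend on that.

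A reader might also infer three stronger points that the documents do not support.

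- **That one failed sample certainly removes a participant.** This is one reading. The 27.6% and 56% figures need that reading and the assumed rates. If failures cluster in a few people, fewer participants are affected at the same overall rate.
- **That dropping one-treatment participants wastes much information.** Step 4 shows that it changes nothing in the planned fixed-block analysis and costs little against a random-participant model unless the correlation is low. Fluoride-only data are kept for the tertiary analyses anyway.
- **That losses fall mainly on hyposalivation participants and shift the analysed population toward normal flow.** No loss rate by flow group is given. Unstimulated flow under 0.1 mL/min for 5 min yields under 0.5 mL of saliva, but that concerns secondary endpoints and only one of the two hyposalivation criteria. No minimum assay volume is stated, and section 8.1 specifies microanalysis electrodes. The primary endpoint uses plaque scraped from teeth. Section 2.3.1 says the time without drinking may trouble low-flow participants more, but it then allows water and records a deviation. More frequent loss in this group is possible, mainly for saliva; it is not shown.

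**Conclusion.** The concern stands in a limited form. Followed literally, 9.3 discards intact pairs from anyone who leaves the last visit early, and 9.4.2 and 9.4.3 do the same after one failed sample if they apply at participant level. Under the assumed 2% or 5% independent failure rates, the choice of reading moves the loss from 4.0% or 9.8% of participants to 27.6% or 56%, with the one-phase AUC between at 14.9% or 33.7%. These are illustrations of scale, not predictions. The consequence is lost precision in a design with no spare participants after its own attrition allowance. The documents do not establish bias by salivary flow. Since the primary objective names hyposalivation, exclusions should still be reported by flow group.

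**What to change.** 1. In 9.3, 9.4.2 and 9.4.3, include every participant who has a result under both treatments for the given endpoint, phase and timepoint. Exclude only the affected timepoint and phase.
2. State in advance how an AUC with one missing timepoint is handled, separately for a middle and a final timepoint. Keep the per-participant concentration AUC as the endpoint; an AUC built from log-scale fitted means would be a different quantity.
3. As a sensitivity analysis, fit a log-scale mixed model to all available data, with treatment, time, treatment-by-time and period as fixed effects and participant and participant-by-visit as random effects.
4. Also report the completer analysis of variance, and tabulate exclusions by flow group and by treatment sequence.

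The cost is SAP wording and some extra analysis, with no new data. The number of participants will differ between timepoints and must be shown for each comparison. The mixed model assumes that data are missing at random, which is one reason to keep it as a sensitivity analysis.
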